## 7. POTENTIAL RISKS AND TOXICITY MONITORING

VIR-7831 has been administered in a Lead-In study phase (based on the 1:1 randomization scheme; overall N = 21) and was generally well tolerated as a single IV infusion at a dose of 500 mg. No subjects died or discontinued from the study due to adverse events (AEs). Based on safety assessment of unblinded Lead-In data, the Independent Data Monitoring Committee (IDMC) recommended initiation of the Expansion study phase. The ongoing Phase 1/2/3 double-blind, placebo-controlled, randomized study enrolled 1,057 non-hospitalized patients with COVID-19 (COMET-ICE). The safety of VIR-7831 is primarily based on an interim analysis from 868 patients through Day 15. All patients received a single 500-mg infusion of VIR-7831 (N = 430) or placebo (N = 438). Two patients experienced treatment interruptions due to infusion site extravasation; infusion was completed for each. Infusion-related reactions, including immediate hypersensitivity reactions, have been observed in 1% of patients treated with VIR-7831 and 1% of patients treated with placebo in COMET-ICE. Reported events that started within 24 hours of study treatment were pyrexia, chills, dizziness, dyspnea, pruritus, rash, and infusion-related reactions; all events were Grade 1 (mild) or Grade 2 (moderate). One case of anaphylaxis was reported following VIR-7831 infusion in a study in hospitalized patients; the infusion was immediately discontinued, and the patient received epinephrine. The event resolved but recurred within 2 hours; the patient received another dose of epinephrine and improved with no additional reactions. Other serious infusion-related reactions (including immediate hypersensitivity reactions) reported following VIR-7831 infusion in the hospitalized study included Grade 3 (serious) or Grade 4 (life-threatening) bronchospasm and shortness of breath. These events were also reported following infusion of placebo. The most common treatment-emergent adverse events observed in the VIR-7831 treatment group in COMET-ICE were rash (2%) and diarrhea (1%), all of which were Grade 1 (mild) or Grade 2 (moderate). No other treatment-emergent adverse events were reported at a higher rate with VIR-7831 compared to placebo. The 250 mg and 500 mg IM doses were evaluated in COMET-TAIL (NCT04913675). So far, reported AEs were not found to be dose-dependent, suggesting a large increase in rate of AEs with 2000 mg IV of sotrovimab is unlikely. We will monitor all subjects for at least 60 minutes (120 minutes for lead-in participants) post-infusion.

Antibody-dependent enhancement of disease and anti-drug antibodies have not been observed *in vitro*, in animal models, or in clinical studies thus far with VIR-7831(25, 26). Participants will receive a phone call at week 36 to monitor for the development of antibody-dependent enhancement of disease. There is currently no available PK or immunogenicity data on a 2000 mg IV dose. Since sotrovimab exhibits dose proportional PK, exposures would be expected to be dose proportional between a 500 mg and 2000 mg IV doses. In the GLP repeat dose IV monkey toxicology study there were no toxicity findings at doses up to 500 mg/kg, the highest dose tested and the no-observed-adverse-effect-level (NOAEL). Assuming dose proportional increase in exposures at 2000 mg, sotrovimab Cmax and area under the curve (AUC) in patients are expected to be 15.5 and 13.5-fold lower than Cmax and AUC values from the toxicology study at the NOAEL, therefore, supporting the evaluation of sotrovimab at the higher clinical dose of 2000 mg IV. Sotrovimab is also considered low risk for immunogenicity based on intrinsic product characteristics (i.e., quality of GMP manufacturing controls and release specifications), extrinsic factors (i.e., administered as a single dose) and patient population (i.e., no apparent heightened risk of immune response). Limited preliminary analysis of immunogenicity data through Day 29 is available from 391 and 38 subjects given 500 mg IV in COMET-ICE and Japan-PK studies, respectively. To date, the incidence of treatment-emergent ADA responses has remained low, with no detectable impact on safety or efficacy. These clinical findings align with the low immunogenicity risk profile and the risk

prediction would not be expected to change substantially at higher doses when the product is administered as a single dose by the same route.

Drawing blood is a routine part of transplant care but can cause bleeding, bruising, pain, soreness, redness, swelling, itching, and/or muscle damage at the site where blood samples are taken. Rarely an infection at the site where blood samples are taken may occur or a blood clot may form. There is also the risk of fainting, dizziness, and anemia (low numbers of red blood cells).

Nasal swab sampling can result in discomfort or pressure during the procedure.

There may be risks of loss of privacy and confidentiality. All blood and swab samples will be given a code and stored securely.

## **7.1 Management of Toxicities**

In the event of side effects attributed to the infusion or otherwise, patients should receive medical treatment as appropriate for the physiological abnormalities. Investigators and clinicians will be instructed to discontinue IV infusions for participants who develop Grade 3 or higher infusion reactions.

## **8. INFORMED CONSENT OF SUBJECT**

Potentially eligible participants will be pre-screened and they or their legally authorized representative contacted to establish interest in the study. If interested, we will arrange a consent meeting in person during a video or phone call based on the preferences of the patient.

The key information about the purpose of the study, the procedures and experimental aspects of the study, the risks and discomforts, and alternative treatment will be presented to the participant.

Participants will be given sufficient time to consider participation in the study. Participants will be asked to sign the consent prior to starting any study procedures. Consent from the patient will be obtained using forms approved by the Fred Hutchinson Cancer Center Institutional Research Board (FHCRC IRB). Once signed, a copy of the informed consent form will be given to the participant for their records. Participants may withdraw consent at any time throughout the course of the study. The rights and welfare of the subject will be protected by emphasizing to them that the quality of medical care will not be adversely affected if they decline/withdraw from the study.

Patients will initially be screened prior to their scheduled transplant. Enrollment will occur when data are reviewed for all inclusion and exclusion criteria by the study and the participant signs consent for infusion. A unique study number will be allocated to each patient and a log of enrolled patients will be maintained.

## **9. CLINICAL AND LABORATORY EVALUATIONS**

A tabular schedule of events is provided in **Appendix A**. The proposed days of all treatments and assessments are approximate and may vary due to scheduling, clinical or other factors.

## **9.1 Evaluations of enrolled patients**

The consent and HIPAA authorization must be signed before any non-standard of care evaluations, including the first blood draw and nasal swab are performed. For patients who have consented, the following will be performed starting prior to infusion:

### **Questionnaires:**

- 1) Participants will complete a weekly symptom questionnaire prior to mAb administration for a total 24 weeks. This questionnaire will be administered through a secure REDCap form and includes questions asking about eye, ear, nose, mouth/throat, sensory, chest, gastrointestinal, skin, muscle/joint, and general/constitutional symptoms. Participants that report one or more nose or chest symptoms will be asked to submit a blood and nasal swab specimen within 48 hours of symptom onset. This would allow for testing for SARS-CoV-2 infection by PCR.

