**Biomarker Assessments:** Immediately prior to mAb administration and at the end-of-infusion, weekly up to week 4, monthly up to week 12, and at week 24 after mAb administration, blood will be drawn by venipuncture (10-20 mL per blood draw) by nursing, a phlebotomist, or trained study staff. At week 12, and monthly thereafter to the end of primary end-point (week 24), blood is self-collected using a TASSO device and by venous blood draw. Nasal specimens will be collected by mid-nasal foam swab at the same time-points as blood draws. Nasal swabs and blood via TASSO (or venous blood draw) will also be collected off-schedule for SARS-CoV-2 PCR and antibody testing as needed based on respiratory symptoms (answering yes to one or more of the nose or chest symptoms) within 48 hours of symptom of symptom onset, up to week 36. If positive for SARS-CoV-2, weekly nasal swabs will be obtained longitudinally for SARS-CoV-2 PCR until negative or until week 36. Serum, plasma, or nasal swabs will be processed and stored at either 4°C, at -20°C, or at -70°C until use, as appropriate. Testing will include serum and nasal total IgG, VIR-7831, SARS-CoV-2-specific IgG, SARS-CoV-2 neutralization titers, and anti-drug antibodies. Testing will be performed at the Fred Hutch, UW, or by Vir Biotechnology.

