## 4.1 Overall Study Design

**Figure 1: Overview of study design and timeline.**

Participants will be screened, consented, and enrolled prior to transplant. Clinical evaluation will occur immediately prior to mAb administration. Participants will complete a weekly symptom questionnaire prior to and weekly after mAb administration for a total 36 weeks. Safety assessments will be performed with routine labs as part of standard stem cell transplant care. mAb will be administered intravenously within seven days of the start of conditioning, and the mAb will be infused at least 24 hours prior to the start of conditioning, i.e. mAb infusion will occur within 1-7 days prior to conditioning. Immediately prior to mAb administration (Pre), at the end-of-infusion (\* in the schematic), weekly up to week 4, monthly up to week 12, and at week 24 after mAb administration, blood will be collected by venipuncture or from a central venous catheter if one is available (10-20 mL per blood draw). At week 12, and monthly thereafter to the end of the primary end-point (week 24), blood will be self-collected using a TASSO device if the participant is unable to return for a venous blood draw. Each timepoint for blood collection will utilize two TASSO devices (or one TASSO+ device). If a participant can present in clinic or is in the hospital, blood collection by venipuncture or from a central venous catheter is permitted instead of using a TASSO device. Nasal specimens will be collected by mid-nasal foam swab at the same time-points as blood draws for antibody testing. Additional nasal swabs may also be collected off-schedule as needed based on reporting of respiratory symptoms on the weekly questionnaire, up to week 36. If positive for SARS-CoV-2, weekly nasal swabs will be obtained longitudinally for SARS-CoV-2 PCR until negative or until week 36. If a participant can present in clinic or is in the hospital, blood can be collected by venipuncture or from a central venous catheter instead of by a TASSO device. Routine nasal swabs collected as part of standard clinical care for SARS-CoV-2 surveillance by PCR post-transplant are not shown. At week 36 (not shown), participants will receive a follow-up phone call to assess for the development of antibody dependent enhancement if they had COVID-19.

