### **Research samples:**

- 1) Blood: All blood specimens are collected for the PK, neutralization, and IgG assays. Immediately prior to mAb administration, at the end-of-infusion, weekly up to week 4, monthly up to week 12, and at week 24 after mAb administration, blood will be collected by venipuncture (10-20 mL per blood draw). Blood drawn from a central venous catheter is permitted. Blood from venipuncture or a central venous catheter will be collected by inpatient nursing, outpatient nursing, phlebotomy, or the study team. If the participant is unable to return to the clinic or hospital for their last blood draw (week 24), we may provide a kit including blood collection tubes so a blood draw can be performed at the participant's local phlebotomy clinic or lab and shipped back to the study site. At week 12, and monthly thereafter to the last blood draw (week 24), blood will be by venous blood draw and self-collected using a TASSO-SST or TASSO+ device. The Tasso™ (Tasso Inc., Seattle WA) device is optimized for needle-free self-collection of blood at home. The TASSO-SST and TASSO+ devices can collect up to 300 µL and 600 µL, respectively, of whole blood from capillaries that can be spun down to serum. For each TASSO time-point, blood will be collected in either two TASSO-SST devices or one TASSO+ device. Each participant will be provided with a backup TASSO device for each TASSO collection time-point in case of device failure (expected 15% failure rate). We have experience using this technology with ongoing COVID-19 antibody testing studies at FHCRC (249 subjects and 2,289 devices). According to the manufacturer, the device has been used in over 5000 subjects since 2004 without any known severe events. The risk for participants is minimal and comparable to the procedures (lancing) for monitoring blood sugar levels. Additional blood may also be collected off-schedule as needed based on reporting of respiratory symptoms (one or more nose or chest symptoms) on the weekly questionnaire (if a specimen is not already scheduled to be collected within a week) for PK, neutralization, and IgG assays. Additional blood samples may also be requested due to inadequate collection or issues related to mail service delivery. Samples will be processed and stored at -20°C or -70°C until use, as appropriate.

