2) Nasal specimens: Sample collection kits will be provided for the collection, handling, and shipping of samples to the [name] laboratory. Participants will self-collect mid-nasal swabs using a foam swab at the same time-points as blood draws. We have compared the performance of self-collected mid-nasal swabs to nasopharyngeal swabs collected by a medical professional and have observed high concordance (Table 2). In addition, we have found high concordance in the use of the mid-nasal foam swabs with nasal washes and flocked swabs for the detection of respiratory viruses (27, 28). Additional nasal swabs may also be collected off-schedule as needed based on reporting of respiratory symptoms (one or more nose or chest symptoms) on the weekly questionnaire within 48 hours of symptom onset, up to week 36. If positive for SARS-CoV-2, weekly nasal swabs will be obtained longitudinally for SARS-CoV-2 PCR until negative or until week 36. Samples will be processed and stored at -20°C or -70°C until use, as appropriate, for SARS-CoV-2 PCR testing and also potentially for antibody testing.

		Nasopharyngeal	
		Positive	Negative
Self-collected	Positive	36	0
	Negative	0	117
	Inconclusive	1	1

Samples collected in the inpatient unit or outpatient infusion center will be picked up by a member of the study team and brought to the [name] Lab on the same day of collection. Samples collected at home will be shipped overnight via FedEx to the [name] Lab.

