E Nasal swabs are self-collected for antibody testing. Additional nasal swabs may also be collected off-schedule as needed based on reporting of respiratory symptoms on the weekly questionnaire within 48 hours of symptom onset, up to week 36. If positive for SARS-CoV-2, weekly nasal swabs will be obtained longitudinally for SARS-CoV-2 PCR until negative or until week 36. Weekly nasal swabs collected as part of standard clinical care up to day +100 post-transplant for PCR surveillance of SARS-CoV-2 are not shown.

F Questionnaires are completed on a secure REDCap form available online.

G Blood pressure, heart rate, breathing rate, oxygen saturation, temperature collected prior to dose administration and at the end of the IV infusion of study drug and every hour during the observation period.

H Infusion will be performed either inpatient or in an outpatient infusion center with clinical staff present on the unit (either MD, advanced practice provider, or nursing staff).

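### Symptom-triggered specimens are due within 48 hours of onset but are triggered by a weekly questionnaire, so only about 2 in 7 questionnaire-triggered specimens can be on time, even with immediate collection

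*Combined protocol and SAP*

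**What the plan says.** Three places tie an off-schedule specimen to the weekly questionnaire and count the time limit from onset.

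- Section 9.1, Questionnaires: "Participants will complete a weekly symptom questionnaire prior to mAb administration for a total 24 weeks". Those who report at least one nose or chest symptom "will be asked to submit a blood and nasal swab specimen within 48 hours of symptom onset".
- Section 9.1, Research samples (nasal specimens): extra swabs depend on symptoms reported "on the weekly questionnaire within 48 hours of symptom onset, up to week 36".
- Appendix A, footnote E: extra swabs depend on "reporting of respiratory symptoms on the weekly questionnaire within 48 hours of symptom onset".

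The synopsis (Biomarker Assessments) sets the same 48-hour limit and makes the trigger a yes answer to a nose or chest item. Section 4.1 and the blood item of Section 9.1 also name the weekly questionnaire as the trigger but give no 48-hour limit. The blood item waives the extra sample "if a specimen is not already scheduled to be collected within a week".

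No section asks participants to report or swab on the day a symptom starts, provides a daily symptom check, or counts the 48 hours from the report.

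**The concern.** A weekly instrument cannot reliably feed a two-day window that opens at onset. A participant whose cough starts the day after one questionnaire reports it about six days later, when the window has been closed for about four days. The text does not say what staff should then do: take a late specimen, skip it or record a deviation. Coordinators may choose differently.

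These swabs serve secondary objective 2, the frequency of breakthrough infection. Viral sequencing and the weekly follow-up swabs both start from a positive PCR. With 50 participants, breakthrough infections may be few, so the timing of each swab matters.

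**Working it through.** The plan states no expected share of onsets sampled in time, so there is no figure to reproduce.

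**Inputs**
- Window: 2 days from onset (Section 9.1; Appendix A, footnote E; synopsis).
- Questionnaire interval: 7 days (Section 9.1).
- Onset within the week: not given; assumed uniform.
- Delay *d* from report to collection: not given; 0 to 2 days shown.
- Trigger: the questionnaire only, relaxed in step 3.

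**Step 1. Share in window** = max(0, 2 − *d*)/7.

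| Delay *d* (days) | Share in window |
|---|---|
| 0 | 2/7 = 28.6% |
| 0.5 | 1.5/7 = 21.4% |
| 1 | 1/7 = 14.3% |
| 1.5 | 0.5/7 = 7.1% |
| 2 | 0% |

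The lag from onset to the next questionnaire averages 7/2 = 3.5 days, with a maximum of 7.

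**Step 2. Appendix A visit windows.** Questionnaire dates may move by ±3 days to week 14 and ±5 days from week 15. A simulation of 24 questionnaires, each shifted uniformly within its window, gives 27.8% with no delay, against 28.5% for exact weekly dates. With a one-day delay the figures are 14.1% and 14.3%. The visit windows barely change the result.

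**Step 3. Relaxing the assumptions**
- Reading 48 hours as calendar days 0 to +2: 3/7 = 42.9%.
- 80% questionnaire completion (assumed): 0.8 × 2/7 = 22.9%.
- A share *s* of participants reporting at onset unprompted (assumed): *s* + (1 − *s*) × 2/7. This gives 35.7% at *s* = 10%, 46.4% at 25% and 64.3% at 50%.

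**Step 4. When it matters.** Section 9.2 takes weekly surveillance PCR results from the medical record to day +30 (autologous) or day +100 (allogeneic) after transplant. Symptom swabs run to week 36, which is 36 × 7 = 252 days after infusion. Let *g* be the number of days from infusion to transplant; the plan gives no single figure for it. The period without routine surveillance is then 252 − 30 − *g* = 222 − *g* days (autologous) or 252 − 100 − *g* = 152 − *g* days (allogeneic).

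**Step 5. Effect on the blood level.** The fall in concentration over a 3.5-day delay is 1 − 2^(−3.5/half-life). With the anticipated half-life of up to 3 months (Section 12.3, taken as 90 days) it is about 3%. With the 7 to 10 days that Section 2 cites for other antibodies in transplant recipients it is 29% to 22%.

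**The case against.** The strongest reply is that detection does not rest on this swab alone. Routine surveillance covers the early months, and Section 9.2 lets the study supply weekly swabs if that practice stops. Section 9.1 also has infection history reviewed monthly to week 24. This stands, and it limits the concern mainly to the period after surveillance ends. It does not remove the concern: Section 12.3 expects breakthrough chiefly towards the end of the study, as antibody levels wane.

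A second reply is that other routes exist. Section 9.2 allows a second swab on symptoms without naming the questionnaire. Appendix A, footnote D, allows the spare TASSO device to be used for symptoms. Section 6.1.3 asks participants to call about adverse events, which Section 10.1 defines broadly enough to include a new cough. So 2/7 is not a hard cap on all sampling. But none of these routes is written as a trigger between questionnaires, and even if half of participants reported unprompted the share would be 64%.

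A reader might also infer four stronger points that the documents do not support.

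- *Most episodes would go unsampled or become deviations.* Section 9 calls assessment days approximate, and no section refuses a late specimen or calls it a deviation.
- *Breakthrough infections are shown to be undercounted.* The documents give no duration of PCR positivity. Following positives weekly until negative implies that positivity can outlast a week.
- *The visit windows make matters much worse.* That takes one unusually long gap between questionnaires as typical; step 2 shows that long and short gaps nearly cancel.
- *Assessment of antibody-dependent enhancement is weakened.* It rests on the week-36 call (Sections 4.1 and 7), not on a 48-hour swab.

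The loss to the blood sample should not be overstated either. No section requires a level at the moment of onset, and the waiver in the blood item of Section 9.1 tolerates timing within about a week.

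**Conclusion.** The point holds in a limited form. As written, the 48-hour rule can be met for about 2 in 7 (29%) of questionnaire-triggered specimens, or 14% if collection takes a day. This assumes uniform onset, on-time completion and the questionnaire as the only trigger. The rule conflicts with its own trigger, so this is more than a missing detail.

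The consequence is late or inconsistently handled symptom-triggered sampling, mainly after day +30 (autologous) or day +100 (allogeneic). It affects breakthrough detection and variant sequencing. Undercounting is possible but cannot be sized from the documents. The change should be made, but it concerns a secondary objective.

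**What to change.** In the synopsis (Biomarker Assessments), both places in Section 9.1 and Appendix A footnote E:

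1. Tell participants to report a new nose or chest symptom, or self-swab from the home kit, on the day it starts, without waiting for the questionnaire. This is the key change; moving the window alone would make the rule workable but leave sampling late.
2. As a backstop, require collection within 48 hours of the report.
3. Record the onset date, so that the delay from onset to swab can be reported.

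State how the paired blood sample is obtained. TASSO devices are scheduled only from week 12, so the spare device can serve only from then; before that a venous draw is needed.

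In the same edit, reconcile the questionnaire's length. Section 9.1 and the synopsis give 24 weeks, while Section 4.1 says "Participants will complete a weekly symptom questionnaire prior to and weekly after mAb administration for a total 36 weeks". Under the 24-week version, symptom swabs in weeks 24 to 36 have no questionnaire trigger at all.

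The cost is wording in four places, one line in the participant instructions and one data field, plus some unscheduled contacts and swabs. Self-collection kits and the online form already exist.
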